### **6.2.3 Duration / Treatment Day / Study Day**

	Sponsor:	Sensorion
	Protocol Number:	SENS 401-201
STATISTICAL ANALYSIS PLAN. PHASE 2-3-4		

Treatment day, which is to be used for safety analyses, will be calculated as the number of days from first dose of study drug:

- date of event – date of first dose of study drug + 1, for events on or after first dose
- date of event – date of first dose of study drug, for events before first dose

Study day, which is to be used for efficacy analyses, will be calculated as the number of days from date of randomization:

- date of event – date of randomization + 1, for events on or after randomization
- date of event – date of randomization, for events before randomization

#### **6.2.4 Conventions for Missing and Partial Dates**

All rules explained below for partial / missing dates will be followed unless contradicted by any other data recorded on the electronic Case Report Form (eCRF).

All dates presented in the individual subject listings will be as recorded on the eCRF (i.e., not completed as per the below rules).

#### **6.2.5 Missing / Partial Start / Stop Date of Adverse Events (AE) and Concomitant Medications**

Missing and partial start and stop date will be imputed for analysis purposes as follows.

##### **Partial or missing stop date will be imputed as follows:**

If the stop date is completely missing and the event has resolved, or the subject has stopped taking the concomitant medication, the stop date will be imputed as the date of the subject’s last clinic visit in the study.

- If only the year is known, the stop date will be imputed as “31-Dec” of that year or as the date of the subject’s last clinic visit in the study if in the same year.
- If the month and year are known, the stop date will be imputed as the last day of that month unless the stop date corresponds to the same month as the subject’s last clinic visit in which case the date of subject’s last clinic visit in the study will be used instead.

##### **Missing start date will be imputed as follows:**

- If the stop date occurs on or after the start of study drug or the event/concomitant medication is ongoing, the start date will be imputed as the date of the first dose of study drug.

	Sponsor:	Sensorion
	Protocol Number:	SENS 401-201
STATISTICAL ANALYSIS PLAN, PHASE 2-3-4		

- If the stop date occurs before the start of study drug, the start date of the event/concomitant medication will be imputed as the subject’s screening date or the stop date of the event/concomitant medication whichever the earlier.

**Partial start date (year present, but month and day missing)**

- If the stop date occurs on or after the start of study drug or the event/concomitant medication is ongoing, and the year is the same as the year of first dosing the start date will be imputed as “01-Jan” of the same year or the date of the first dose of study drug whichever is latest. If the year is different from the year of first dosing “01-Jan” will be used.
- If the stop date occurs before the start of study drug, the start date of the event/concomitant medication will be imputed as the “01-Jan” of the same year.

**Partial start date (month and year present, but day missing)**

- If the stop date occurs on or after the start of study drug or the event/concomitant medication is ongoing, the start date will be imputed as the first day of the same month and year unless this partial start date is in same month as the first dose of study drug in which case the date of first dose of study drug will be used.
- If the stop date occurs before the start of study drug, the start date will be imputed as the first day of the month and year of the partial stop date.

If the start time is missing it will be imputed only in the case where the start date of the concomitant medication/event corresponds to the date of the first dose of study drug. The time will be imputed as the same time as the first dose of study drug. In all other cases the time will not be imputed.

**6.2.6 Missing Last Dates of Study Drug Dosing**

If the date of last dose of study drug is completely missing, then the date of last dose of study drug will be taken for analysis purposes as the date when the subject would have run out of study drug assuming full compliance from the date the study drug was last dispensed or the date of subject’s last clinic visit in the study or early withdrawal or death whichever the earlier.

If only the month and year of the last dose was recorded, then the date of last dosing will be taken for analysis purposes as the date the subject would have run out of study drug assuming full compliance from the date the study drug was last dispensed, the last day of the month of the recorded last dose or the date of subject’s last clinic visit in the study or early withdrawal or death whichever the earlier.

**6.2.7 Missing Diagnosis Dates**

	Sponsor:	Sensorion
	Protocol Number:	SENS 401-201
STATISTICAL ANALYSIS PLAN. PHASE 2-3-4		

If the month and year are present but the day is missing, the diagnosis date will be set to first day of the relevant month. If only the year is recorded the diagnosis date will be set as “01-Jan” for that year.

**6.2.8 Exposure to Study Drug**

Exposure to study drug will be calculated as follows from the date of last dosing minus the first day of dosing + 1. The exposure calculation will not take into account breaks in therapy.

**6.2.9 Inexact Values**

In the case where a variable is recorded as “> x”, “≥ x”, “< x” or “≤ x”, a value of x will be taken for analysis purposes.

**6.2.10 Height/Weight/Temperature**

When height is collected in inches (in), the measurements will be converted to centimeters (cm) using the following rule:

$$\text{Height (cm)} = 2.54 * \text{height (in)}$$

When weight is collected in pounds (lbs), the measurements will be converted to kilograms (kg) using the following rule:

$$\text{Weight (kg)} = 0.45359237 * \text{weight (lbs)}$$

When temperature is collected in Fahrenheit degrees (F), the measurements will be converted to Celsius degrees (C) using the following rule:

$$\text{Temperature (C)} = (\text{temperature (F)} - 32) / 1.8$$

**6.2.11 Electrocardiogram (ECG) Data**

The Banook Group will prepare a separate ECG SAP for the analysis of the ECG data. .

**6.2.12 Columbia-Suicide Severity Rating Scale (C-SSRS)**

The following outcomes are C-SSRS categories and have binary responses (yes/no). The categories have been re-ordered from the actual scale to facilitate the definition of composite endpoints:

Category 1	Wish to be Dead
------------	-----------------

	Sponsor:	Sensorion
	Protocol Number:	SENS 401-201
STATISTICAL ANALYSIS PLAN. PHASE 2-3-4		

Category 2	Non-specific Active Suicidal Thoughts
Category 3	Active Suicidal Ideation with Any Methods (Not Plan) without Intent to Act
Category 4	Active Suicidal Ideation with Some Intent to Act, without Specific Plan
Category 5	Active Suicidal Ideation with Specific Plan and Intent
Category 6	Preparatory Acts or Behavior
Category 7	Aborted Attempt
Category 8	Interrupted Attempt
Category 9	Actual Attempt (non-fatal)
Category 10	Suicidal Behavior (Lifetime and Past 12 Months version) / Suicide (Since Last Visit version)

Suicidal Ideation at baseline – A “yes” answer at baseline to any one of the 5 suicidal ideation questions (categories 1-5) on the C-SSRS Lifetime or Past 12 Months version.

Suicidal Behavior at baseline – A “yes” answer at baseline to any one of the 5 suicidal behavior questions (categories 6-10) on the C-SSRS Lifetime or Past 12 Months version.

Suicidal Ideation since baseline – A “yes” answer at any time during double blind treatment to any one of the 5 suicidal ideation questions (categories 1-5) on the C-SSRS Since Last Visit version.

Suicidal Behavior since baseline – A “yes” answer at any time during double blind treatment to any one of the 5 suicidal behavior questions (categories 6-10) on the C-SSRS Since Last Visit version.

There will be no imputation of missing data for C-SSRS.

### 6.2.13 Laboratory data

The following rules will be applied for purposes of unit conversion of WBC differential parameters:

$$\text{Result value (10}^9\text{/L)} = \text{Result value (\%)} * \text{WBC (10}^9\text{/L)}$$

$$\text{Ref Range value (10}^9\text{/L)} = \text{Ref Range value (\%)} * \text{WBC Ref Range value (10}^9\text{/L) min and max}$$

	Sponsor:	Sensorion
	Protocol Number:	SENS 401-201
STATISTICAL ANALYSIS PLAN. PHASE 2-3-4		

### 6.2.14 Randomization Strata

The randomization will be stratified according to the site category (non-ancillary, ancillary), the duration of the hearing loss ( $\geq 24$ hours/ $< 24$  hours) and the intake of corticosteroids (Yes, No).

### 6.2.15 Change from baseline

Change from baseline in absolute terms is defined as the baseline value subtracted from the postbaseline value.

### 6.2.16 Analysis Window

For the analysis of all the efficacy and safety endpoints, the following analysis windows will be used to obtain the analysis visits. For each respective analysis visit, all assessments, either scheduled or unscheduled/repeat, will be considered. The values collected during the study will be mapped to protocol visits according to the windowed times indicated below. Should more than one value fall within the same time window, then the closest value to the planned day will be assigned to the visit. If the values are equidistant to the planned day, the latest value will be retained.

Analysis Visit	Window
Day 7	[Day 5, Day 9] (Day 7 +/- 2 days)
Day 14	[Day 10, Day 18] (Day 14 +/- 4 days)
Day 28	[Day 20, Day 36] (Day 28 +/- 8 days)
Day 84	[Day 60, Day 108] (Day 84 +/- 24 days)

Note: Day in the table is Study Day for efficacy endpoints, Treatment Day for safety endpoints

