## 11 STUDY PROCEDURES

### 11.1 Visits

Study procedures are described in the flow chart (Section 4). The following are general guidance relating to all visits.

Every attempt should be made to complete the follow-up visits during the defined window periods.

A final follow-up visit is required for all patients. In the rare cases the End of Study Visit (V6) cannot occur, any attempt to contact the patient should be recorded on a special contact form, until/unless appropriate information is obtained which will allow completion of final follow-up visit in the e-CRF, even after the anticipated timeframe.

Blood is collected by venipuncture. The exact time of sample collection should be transferred into database and should be collected on the laboratory request form for local blood sampling.

Important note: Any abnormal laboratory value, abnormal ECG parameter, SAE will be immediately rechecked for confirmation before making a decision of permanent discontinuation of IP for the concerned patient.

Patients will be advised to avoid skin exposure to strong sunlight and to wear sunglasses in bright sunlight for the duration of the study and for 1 week after the last dose.

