#### **11.1.7 Unscheduled Visit: Visit 99**

In case of adverse event, abnormal values or dispensation of a replacement IMP kit, an additional visit may be needed to repeat the test or document an adverse event or to dispense a new IMP kit.

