### 6.14.2 Laboratory Data

Descriptive statistics of the observed values and change from baseline (continuous data) will be presented by treatment group and visit for each hematology, serum chemistry, and C-reactive protein parameter. For categorical laboratory parameters, subject counts within each category will be summarized. Shift tables from baseline to each post-baseline visit will also be presented, as applicable.

Each measurement (continuous data) will be classified as below, within, or above normal range, based on ranges supplied by the laboratory used. This study utilizes local laboratories only and therefore each local laboratory will provide its reference ranges. Shift tables in relation to the normal range from baseline to each follow-up visit will be presented.

Moreover, the number and percentage of subjects with treatment-emergent marked laboratory abnormalities will be tabulated for each laboratory parameter for which marked abnormalities are defined in the table below. For a given parameter, percentages will be based on the number of subjects at risk: those not meeting the criterion at baseline (or having a missing baseline value) and having at least one post-baseline value (including post-baseline value after last intake of study drug). The marked laboratory date abnormalities are defined as follows:

		Sponsor:	Sensorion
		Protocol Number:	SENS 401-201
STATISTICAL ANALYSIS PLAN. PHASE 2-3-4			

Category	Lab Test/ Examination Name	Unit	Marked Abnormalities				
			LL	LLL	HH	HHH	HHHH
CHEMISTRY	Alanine Aminotransferase	U/L			>3ULN	>5ULN	>8ULN
CHEMISTRY	Albumin	g/L	<30	<20			
CHEMISTRY	Alkaline Phosphatase	U/L			>2.5ULN	>5ULN	
CHEMISTRY	Aspartate Aminotransferase	U/L			>3ULN	>5ULN	>8ULN
CHEMISTRY	Bilirubin	umol/L			>2ULN	>5ULN	
CHEMISTRY	Calcium	mmol/L	<2.0	<1.75	>2.9	>3.1	
CHEMISTRY	Creatine Kinase	U/L			>5ULN	>10ULN	
CHEMISTRY	Creatinine	mmol/L			>1.5ULN or (>1.5baseline if baseline > ULN)	>3ULN or (>3baseline if baseline>ULN)	
CHEMISTRY	Creatinine Clearance	mL/min/ 1.73m 	<60	<30			
CHEMISTRY	Gamma Glutamyl Transferase	U/L			>2.5ULN	>5ULN	
CHEMISTRY	Glucose	mmol/L	<3.0	<2.2	>8.9	>13.9	
CHEMISTRY	Phosphate	mmol/L	<0.8	<0.6			
CHEMISTRY	Potassium	mmol/L	<3.2	<3.0	>5.5	>6.0	
CHEMISTRY	Sodium	mmol/L	<130		>150	>155	
CHEMISTRY	Triglycerides	mmol/L					
CHEMISTRY	Urate	umol/L			>590	>720	
CHEMISTRY	Urea	mmol/L			>2.5ULN	>5ULN	
HEMATOLOGY	Eosinophils	10  /L			>5.0		

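### For laboratory safety data, the SAP window rule lets a confirmatory recheck displace the abnormal scheduled value, which can only lower abnormal counts in the by-visit shift tables

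*SAP*

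**What the plan says.** SAP 6.2.16 sets one selection rule for the whole analysis: "For the analysis of all the efficacy and safety endpoints, the following analysis windows will be used to obtain the analysis visits". Repeats are admitted on equal terms: "For each respective analysis visit, all assessments, either scheduled or unscheduled/repeat, will be considered". The choice among them is by distance: "Should more than one value fall within the same time window, then the closest value to the planned day will be assigned to the visit". Ties go to the later result: "If the values are equidistant to the planned day, the latest value will be retained". No exception is made for confirmatory repeats.

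Protocol 11.1 gives the main reason why a laboratory repeat would exist: "Any abnormal laboratory value, abnormal ECG parameter, SAE will be immediately rechecked for confirmation before making a decision of permanent discontinuation". A note in Protocol 11.3.2 says the same under the withdrawal criteria. Protocol 12.4.1 asks for a repeat when an abnormal test is judged medically meaningful, and 12.6 when the abnormality is severe. Protocol 11.1.7 allows an unscheduled visit for the purpose: "abnormal values or dispensation of a replacement IMP kit, an additional visit may be needed to repeat the test". None of these sections asks for a normal result to be repeated.

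SAP 6.14.2 builds by-visit descriptive statistics on the selected values, and also this output: "Shift tables in relation to the normal range from baseline to each follow-up visit will be presented".

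**The concern.** A rule that picks the nearest or latest of several results is harmless when the reason for the extra result is unrelated to its value. Here it is related. A laboratory result is repeated because it was abnormal, so the extra candidate appears only beside abnormal scheduled values. If it wins, the shift table shows the recheck instead of the finding that prompted it. A result that was already normal has no competitor and stays.

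At stake is how many patients each by-visit shift table shows moving outside the normal range. In Part 1, with 37 patients per arm, those counts will be small, and one or two patients would change how a row reads.

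**Working it through.** The plan states no figure on this point, so there is none to reproduce. The check applies the rule to the allowed visit days.

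**Inputs.** Post-baseline laboratory tests are at Day 14 ±2 and Day 28 ±3 (Protocol section 4 and 10.2.5), so the allowed visit days are 12–16 and 25–31. The SAP windows are Days 10–18 and 20–36 (6.2.16).

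**Rule.** Let p be the planned day, s the day of the scheduled draw and k the lag to the recheck. The recheck is kept if |s + k − p| ≤ |s − p|, with equality going to the recheck because it is later. Any recheck meeting this condition also lies inside the SAP window.

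- k = 0: both sides are equal, so the recheck is always kept.
- k ≥ 1: the condition holds only if the draw was early by e = p − s > 0 days and k ≤ 2e.

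Counting allowed visit days on which the recheck displaces the scheduled value:

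| Lag k (days) | Requires | Day 14 (12–16) | Day 28 (25–31) |
|---|---|---|---|
| 0 | nothing | 5 of 5 | 7 of 7 |
| 1–2 | e ≥ 1 | 2 of 5 | 3 of 7 |
| 3–4 | e ≥ 2 | 1 of 5 | 2 of 7 |
| 5–6 | e ≥ 3 | 0 of 5 | 1 of 7 |
| 7 | e ≥ 4 | 0 of 5 | 0 of 7 |

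Two examples. With a draw on Day 26 and a recheck on Day 28, the distances are 2 and 0, so the recheck is kept. With a draw on Day 29 and a recheck on Day 30, they are 1 and 2, so the scheduled value stays. The fractions count calendar days; they are probabilities only if visits are spread evenly over the allowed days.

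**Direction.** For the analyte that prompted the recheck, the displaced value was abnormal. The recheck is either abnormal too (count unchanged) or normal (count down by one). The count cannot rise.

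**Means.** Assume a normally distributed analyte with total SD 1, a limit at 1.96 SD, test–retest correlation ρ, and every value above the limit displaced. The mean then moves by −(1 − ρ) × φ(1.96), with φ(1.96) = 0.0584:

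- ρ = 0.5: 0.5 × 0.0584 = 0.029 SD
- ρ = 0.7: 0.3 × 0.0584 = 0.018 SD
- ρ = 0.9: 0.1 × 0.0584 = 0.006 SD

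The ρ values are assumptions. Even under full displacement the shift in the mean is negligible, so the effect falls on the shift-table counts.

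**What other outputs recover.** The marked-abnormality table in SAP 6.14.2 counts patients beyond wide limits, for example ALT above 3 × ULN and alkaline phosphatase above 2.5 × ULN. An ALT between 1 and 3 × ULN is not counted there. Chloride, LDH, total protein, cholesterol and red cell count are in the Protocol 10.2.5 panel but have no row. Platelets show the gap where a recheck is clearly called for: Protocol 11.3.2 acts on confirmed counts below 100,000/mm³ (100 × 10⁹/L), while the marked limit is below 75 × 10⁹/L. A first count between the two would be rechecked, but would not count as marked. SAP 6.14.2 also does not say whether marked counts use all post-baseline values or only the one selected under 6.2.16.

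**The case against.** The strongest reply is that the recheck trigger is narrower than it first looks. The sentence in Protocol 11.1 concerns confirmation before permanent discontinuation; 12.4.1 is limited to medically meaningful results and 12.6 to severe ones. The natural reading is a confirmation step, not a retest of every result outside a local reference range. This stands, and it rules out putting a figure on the loss. A reader might infer that a set share of out-of-range patients disappears from the shift tables, but any such percentage needs a recheck rate, which the documents do not give.

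It can also be said that the abnormal result survives elsewhere. Medically meaningful abnormalities are reported as adverse events, all laboratory data are listed, and clinically significant values have their own listing. The analytes with a discontinuation criterion that are in the routine panel all have a marked-abnormality row, and the analytes without limits are the least likely to be rechecked. This mitigates the problem but does not remove it, because listings are not summaries and sub-threshold changes are not counted as marked.

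Finally, one may prefer the confirmed value on principle, since the protocol treats an abnormal result as provisional. That is a defensible view, but the SAP does not state it, and the rule does not deliver it consistently: the same recheck is kept or discarded according to whether the scheduled draw was early or late.

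Three further inferences are not supported. The rule does not favour the active arms, since it applies alike to all arms under blinding. It does not distort mean changes to any useful degree. It should not be extended to all safety data: ECG has its own SAP (6.2.11), and no repeat trigger is written specifically for vital signs, otoscopy or tympanometry.

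**Conclusion.** The point holds for laboratory data. As written, 6.2.16 discards an abnormal scheduled result whenever a same-day recheck exists. For later rechecks it does so on 2 of 5 or 3 of 7 allowed visit days at lags of 1 to 2 days, and on fewer after that. Because repeats follow abnormal results only, the selection is one-directional and lowers abnormal counts in the by-visit normal-range shift tables.

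Those fractions follow from the documents and are conditional on a recheck being done. How many rechecks will occur, how many on the same day, and how many will return to normal are all unknown, so the total effect cannot be stated. It matters enough to correct before the tables are produced. It does not threaten the trial's main safety conclusions, given the adverse event reporting, marked-abnormality table and listings.

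**What to change.** In SAP 6.2.16, make a separate provision for laboratory safety data, in both parts of the study:

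1. By-visit descriptive statistics and by-visit shift tables use the scheduled value; an unscheduled or repeat value is used only if the scheduled one is missing.
2. Add one shift table per analyte from baseline to the worst post-baseline value, using all results including repeats. This supplements the by-visit tables and does not replace them.
3. State in 6.14.2 that marked-abnormality counts use all post-baseline values, including repeats.

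The cost is SAP wording, a derived worst-value record and one additional table; no new data are needed. The tables will look slightly less favourable and will include some abnormal values that were not confirmed. The safety baseline in 6.2.2 is the last value before dosing, repeats included, so a worst-value table set against it will show more shifts to abnormal in every arm. It should be labelled accordingly and read as a comparison between arms.

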### 6.12.1 Primary Endpoint

The primary endpoint is the change in pure tone audiometry (PTA: average of the hearing threshold of 3 contiguous most affected hearing frequencies in decibels as identified at study entry) on pure tone audiometric air conduction testing in the affected ear from baseline to the end of treatment visit (Visit D28 ± 3).

The 3 most affected contiguous audiometric test frequencies are defined with respect to the unaffected contralateral ear and will be fixed for all further calculations. In case of a pre-existing contralateral hearing loss, the corresponding values of a pre-existing audiogram of the affected ear, if dating back less than 2 years, will be considered as the reference. For all other scenarios (e.g. pre-existing contralateral hearing loss with no audiogram in the past 2 years) the reference frequencies will be set using the ISO 7029;2017 norm values. In case of bilateral acute acoustic trauma leading to sudden sensorineural hearing loss, the most affected ear according to the inclusion criteria will be considered. If both ears are equally affected, the right ear will be considered.

At baseline, if 2 or more sequences of 3 contiguous frequencies are similarly affected, the index sequence with the lower contiguous frequencies will be selected as the reference. Pure tone average frequencies determined at baseline will remain fixed for all evaluations.

If one of the frequencies is missing for post baseline values the PTA will be averaged on 2 out of the 3 identified frequencies. If more than 1 is missing, the PTA will not be calculated.

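### The SAP 6.2.16 windows leave Day 19 unmapped, lose a Visit 3 audiogram that is one day late, and let a value outside D28 ± 3 stand as the primary outcome without saying so or testing it

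*SAP*

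**What the plan says.** SAP 6.2.16 sets four windows: "Day 5, Day 9] (Day 7 +/- 2 days", "Day 10, Day 18] (Day 14 +/- 4 days", "Day 20, Day 36] (Day 28 +/- 8 days" and "Day 60, Day 108] (Day 84 +/- 24 days". Their scope is general: "For the analysis of all the efficacy and safety endpoints, the following analysis windows will be used to obtain the analysis visits". Within it, "all assessments, either scheduled or unscheduled/repeat, will be considered". The selection rule works inside one window only: "Should more than one value fall within the same time window, then the closest value to the planned day will be assigned to the visit". A tie goes to the later value. For efficacy, days are counted from randomisation as Day 1 (SAP 6.2.3).

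The primary endpoint (SAP 6.12.1) is the change in pure tone average (PTA) in "the affected ear from baseline to the end of treatment visit (Visit D28 ± 3". SAP 3.1 and protocol 6.2.1 carry the same ± 3. The protocol flow chart (section 4) allows ± 2 days at Day 7, ± 2 at Day 14, ± 3 at Day 28 and ± 3 at Day 84.

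Three other provisions matter here:

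- Protocol 11.3.1 calls for the Visit 5 assessments when a patient stops treatment before Visit 5.
- The primary repeated-measures model (SAP 6.12.2) uses the windowed Day 7, 14 and 28 visits and assumes data missing at random.
- The copy-reference analysis (SAP 6.12.3) imputes only values that are missing at those visits.

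SAP section 8, which lists changes and clarifications against the protocol, does not mention the windows.

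**The concern.** The window decides which audiogram becomes the primary outcome, so it should cover the days on which audiograms can arise and agree with the endpoint as written. Off-schedule tests are to be expected, because the protocol asks for one at early discontinuation.

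Under the present windows, a one-day difference in the date of that test changes its status from unused to observed primary outcome, and no reason is given. Once a Day 20 value is labelled Day 28, the missing-data sensitivity analysis has nothing to impute for that patient. The one analysis meant to probe early discontinuation therefore passes over the case. Separately, the Day 14, 28 and 84 windows are wider than the protocol's visit tolerances but the Day 7 window is not, so a Visit 3 audiogram one day late leaves the Day 7 cell empty.

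**Working it through.** **1. Reproduce the windows.** 7 ± 2 = [5, 9]; 14 ± 4 = [10, 18]; 28 ± 8 = [20, 36]; 84 ± 24 = [60, 108]. All four match the SAP table and none overlap.

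**2. Find the gaps.** Going day by day from Day 2, the unmapped days are 2–4, 19, 37–59 and everything after 108. Between Day 5 and Day 36 the only gap is Day 19.

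**3. Compare with the endpoint.** D28 ± 3 is Days 25–31, which is 7 days. The window holds 36 − 20 + 1 = 17 days. Outside ± 3 there are 17 − 7 = 10 days: Days 20–24 (five) and Days 32–36 (five).

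**4. Visit 3 one day late.** The protocol window ends on Day 9. A Day 10 audiogram falls under Day 14 at distance |14 − 10| = 4. Visit 4 inside its own protocol window (Days 12–16) is at most 2 days away and wins. If Visit 4 is missed, the Day 10 value becomes the Day 14 value. Either way Day 7 is empty.

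**5. Early discontinuation.** Assume the test is done on the stop day and no later audiogram falls by Day 36.

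| Test on | If Visit 4 was done on Day 14 | If Visit 4 was missed | Day 28 in the copy-reference analysis |
|---|---|---|---|
| Day 18 | not used (distance 4 loses to 0) | used as Day 14 | imputed |
| Day 19 | not used (no window) | not used (no window) | imputed |
| Day 20 | used as Day 28 (distance 8) | used as Day 28 (distance 8) | treated as observed |

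**6. Size, as an illustration only.** The documents give no recovery rate and no visit-timing data. Assume hearing improves by 0.2 to 1 dB per day between Day 20 and Day 28. A Day 20 value standing for Day 28 then misstates that patient's change by 8 × 0.2 = 1.6 dB to 8 × 1 = 8 dB. If 2 of 37 patients in an arm were affected (also assumed), the arm mean moves by 2/37 × 1.6 = 0.09 dB to 2/37 × 8 = 0.43 dB. Part 1 is planned on a 15 dB difference.

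**7. Windows after the change.** With [5, 10], [11, 20] and [21, 36], every day from 5 to 36 is mapped. Day 10 goes to Day 7, and Days 19 and 20 go to Day 14. Day 21 is 7 days from both Day 14 and Day 28 and stays with Day 28. The Day 28 window then holds 16 days, of which 9 (Days 21–24 and 32–36) are still outside ± 3. Contiguous windows alone therefore do not test the endpoint at ± 3; that needs a separate analysis.

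**The case against.** Several stronger readings are tempting, and the documents do not support them.

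- **A reader might infer that Days 10 and 20 go to the farther visit.** That is true in plain days: 3 against 4 for Day 10, and 6 against 8 for Day 20. But each half-width is exactly 2/7 of its planned day (2/7 of 7, 14, 28 and 84 gives 2, 4, 8 and 24), which suggests windows proportional to elapsed time. On that scale the boundaries are √(7 × 14) = 9.9 and √(14 × 28) = 19.8. Day 10 is then nearer Day 14 (14/10 = 1.40 against 10/7 = 1.43), and Day 20 is nearer Day 28 (28/20 = 1.40 against 20/14 = 1.43). The SAP states neither rationale, so this is a choice and not an error. The loss of a one-day-late Visit 3 remains.
- **A reader might infer that the wide Day 28 window breaches the endpoint.** The ± 3 reads as a scheduling tolerance for Visit 5, and analysis windows wider than visit windows are ordinary. An audiogram at a Day 22 discontinuation is arguably that patient's end-of-treatment assessment. This stands. What is missing is a statement of which range governs and an analysis at the range written into the endpoint.
- **A reader might count Days 2–4 as lost data.** No visit is scheduled then, and keeping such early tests out of Day 7 is defensible.
- **Other analyses cover part of this.** Missing visits are handled under missing at random and by copy reference, rescue has its own sensitivity analysis, and all PTA data are listed, so a Day 19 value is unmapped but not destroyed. None of these addresses a Day 20–24 value counted as observed simply because of its date.
- **The protocol sets no analysis windows**, so strictly nothing was changed. Section 8 nevertheless records clarifications as small as a plural made singular, so a note belongs there.

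**Conclusion.** The point holds as a limited, correctable gap in the mapping rules, and the day counts follow directly from the SAP. It arises only when a visit is off schedule or treatment stops early: audiograms on Days 5–9, 12–16 and 25–31 are mapped as intended. A Day 20–24 or 32–36 value serves as Day 28 only when no closer one exists in the window.

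The number of patients concerned cannot be derived from the documents. On the assumed figures above, the shift in an arm mean stays below half a decibel. A similar pattern of late visits or early stops in each arm would tend to cancel in the comparison. The documents therefore do not support a conclusion that the primary result is materially biased. The case for acting is that the rule selects the primary outcome with 37 patients per arm in Part 1, the same SAP serves Part 2, and the remedy uses data already collected.

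**What to change.** 1. In SAP 6.2.16, make the windows contiguous from Day 5 to Day 36: Day 7 = [5, 10], Day 14 = [11, 20], Day 28 = [21, 36]. Leave Days 2–4 unmapped.
2. State in SAP 6.12.1 that the analysis window, not ± 3, selects the Day 28 value.
3. Add to SAP 6.12.3 a repeat of the primary repeated-measures model with the Day 28 value restricted to Days 25–31.
4. Note the window in SAP section 8, and correct the cross-reference in SAP 6.12.2, which cites 6.2.15 for the analysis visits.
5. Keep the separate DMC SAP consistent. It governs the Part 1 week-4 efficacy analysis, its windows are not visible here, and changing one plan alone could give two different analyses of the same endpoint.

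The contiguous windows have limits. A Day 19 value will be used as Day 14 only when no audiogram falls on Days 11–18, and the step from Day 14 to Day 28 moves to between Days 20 and 21. Item 3 is what shows whether values outside ± 3 influence the result.

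The cost is a few lines of SAP text and one extra model run, settled before unblinding, with no new data. The downside is that a few Day 20 values fall under Day 14 instead of Day 28.
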